**Table 9–1: Swelling and tenderness grading**

Grade	Swelling response (44)	Tenderness response (44)
0	None	None
1	Swelling present	Tenderness present

### 9.1.20 Total and nocturnal spinal pain NRS

The pain experienced by AS subjects is adequately measured by 2 separate questions: 1) total pain in the spine due to AS (ie, “How much pain of your spine due to spondylitis do you have?”); and 2) pain in the spine at night due to AS (ie, “How much pain of your spine due to spondylitis do you have at night?”) (Sieper et al, 2009, van der Heijde et al, 2005; CPMP/EWP/556/95). Usually, a 10% difference (ie, a 1 point difference on a NRS ranging from 0 to 10) is considered the MCID used to interpret scores (Dworkin et al, 2008). Pain experienced by axSpA subjects has also been measured with this assessment (Haibel et al, 2008) and is validated (van Tubergen et al, 2015) (see Appendix 18.11).

The pain NRS assessments per visit are described in [Table 5–1](#), [Table 5–2](#), [Table 5–3](#), and [Table 5–6](#).

## 10 ASSESSMENT OF PHARMACOKINETICS, EXPLORATORY BIOMARKERS, AND PHARMACOGENOMICS VARIABLES

Plasma samples for the measurement of CZP concentrations will be taken at Baseline and Weeks 1, 2, 4, 12, 24, 36, 52/WD, and at the FU visit (8 weeks after the Week 52/WD visit). These plasma samples may be used additionally for analyses of CZP and its constituent moieties using alternative methods and the results of those analyses may be reported separately.

These plasma samples may be used for possible analyses of exploratory biomarkers which might include, but are not limited to: MMP-3, BMP-2, -4 and -7, WNT1, WISP, Gremlin, DKK1, Sclerostin, Hedgehog proteins (Shh, Ihh, Dhh), Collagen turnover/cleavage products, collagen type X, VEGF, citrullinated vimentin fragments, cytokines: IL13, IL17 A and F, IL23, IL34, (TGF- $\beta$ , M-CSF, GM-CSF, CSF-1, sCSF1r levels. The results of the analyses of CZP and its constituent moieties from alternative methods may be reported separately.

For subjects participating in the optional substudy, blood samples will be drawn for possible genetics/epigenetics, genomic, proteomics and metabolomic analysis at Baseline and Week 12,

and for genomic, proteomics, and metabolomic analysis only, at Week 4 and Week 52/WD to enable exploratory evaluation of biomarkers relative to drug treatment, disease biology and inflammatory and immune response processes.

Samples will be moved from the Central Laboratory (ACM) at the end of the study to a long-term storage facility - BioStorage Technologies, GmbH - and will be stored at -80°C at a central biorepository for up to 20 years.

## 11 ASSESSMENT OF IMMUNOGENICITY VARIABLES

Plasma samples for the measurement of anti-CZP antibodies and potentially neutralizing antibodies will be taken at Baseline and Weeks 1, 2, 4, 12, 24, 36, 52/WD, and the FU visit (8 weeks after the Week 52/WD visit).

The sampling, handling, and shipment of samples will be performed as detailed in the Laboratory Manual.

## 12 ASSESSMENT OF SAFETY

Safety variables to be assessed are physical examinations, AEs, vital signs, and measurements of laboratory parameters.

Adverse events will be solicited at every visit, and recorded and coded according to the latest version of the Medical Dictionary for Regulatory Activities (MedDRA®) criteria.

Physical examination findings will be recorded in the CRF only at Screening. Clinically important abnormal changes in subsequent physical examinations will be recorded as AEs at all visits from Baseline to the FU visit.

Clinical laboratory values (hematology, biochemistry, urinalysis) will be collected and assessed at Screening, Baseline, Weeks 2, 4, 8, 12, 24, 36, at the end of study completion at Week 52/WD visit and at the FU visit (8 weeks after the Week 52/WD visit). In addition, clinical laboratory values will be collected and assessed at study visits during the administration of open-label CZP in subjects who withdraw from the double-blind study treatment.

Furthermore, CRP will be collected and assessed either in a blinded or open manner at Screening, 3 to 5 days before Baseline, Weeks 2, 4, 8, 12, 16, 20, 24, 28, 32, 36, 40, 44, 48, and at the end of study completion at Week 52/WD visit and at the FU visit (8 weeks after the Week 52/WD visit).

At Screening, all subjects will have an IGRA test (QuantiFERON® TB test or Elispot® test, when the QuantiFERON test indicated is not available), and a chest x-ray reading (or, if done, computed tomography of the chest) which must be reported consistent with standard clinical reporting practice by an experienced qualified TB specialist, radiologist, or a pulmonologist, who is specifically required to look for signs of active TB or signs of past/inactive TB infection. A chest x-ray will not be done at Screening if a chest x-ray (or computed tomography of the chest) was done within 3 months prior to the Screening visit. The official report of the imaging must specifically indicate the absence of findings suggestive of current active TB or prior inactive TB. In addition to a physical examination done intermittently throughout the study, subjects will be evaluated at Screening, Baseline, and every 12 weeks thereafter up to Week 36 and including the Week 52/WD visit, for signs and symptoms of LTB or active TB infection and risk factors for exposure to TB using the TB questionnaire.

---

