## 5.2 Schedule of study assessments

The Schedule of assessments is shown in [Table 5–1](#) for subjects who complete 52 weeks of treatment on either CZP 200mg Q2W or placebo.

In order to optimize the treatment the Investigator may adjust the background medication in accordance with the specifications described in [Table 7–1](#).

At any time during the study course, but preferably not before Week 12, the Investigator may discontinue the double-blind study treatment and start open-label treatment with either CZP (which will be provided free of charge by UCB) or an alternative drug (eg, other treatment [including biologics]). [Table 5–2](#) shows the schedule of assessments for subjects receiving open-label treatment with CZP and [Table 5–3](#) shows the schedule of assessments for subjects receiving an alternative treatment (not CZP).

[Table 5–6](#) shows the schedule of assessments for subjects participating in the SFE Period.

This document cannot be used to support any marketing authorization application and any extension or variations thereof.

REDACTED COPY

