## **7.9 Blinding**

Due to differences in presentation and viscosity between CZP and placebo, special precautions will be taken in order to ensure blinding during the Double-Blind Period of the study. The subject will receive the IMP throughout the study duration for each single administration in a sealed box with PFS containing either CZP 200mg or placebo. Packaging and labeling will be done in a way to ensure that the provided box including the PFS will not provide any information about the assigned treatment (CZP 200mg or placebo). Administration of the IMP will be done according to the schedule of study assessments (Table 5-1) either on-site by appropriately trained unblinded study personnel or at home by the subject him/herself. Pharmacokinetic and antibody data will be provided only after the study is unblinded.

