## 8.2 Baseline visit (Week 0)

Subjects agreeing to participate in the study, after giving signed informed consent, will have the following procedures performed/recorded prior to study drug administration:

- Review of inclusion/exclusion criteria. Note: The qualifying CRP levels from the Screening Period 3 to 5 days before Baseline will be used for the inclusion criteria review and for randomization stratification. The result of the centrally read MRI and X-ray must be available for the inclusion criteria review.
- Vital signs (pulse rate, systolic and diastolic blood pressure, temperature, and respiration rate)
- Blood samples (subjects should be encouraged to be under fasting conditions, the same condition [fasting or not fasting] should be applied at Week 52) will be collected for hematology and biochemistry analyses (biochemistry assessment will include the measurement of apolipoprotein (Apo) A1, ApoB, lipoprotein(a), and glycated hemoglobin [HbA1c])
- Urine will be collected for urinalysis and for a urine pregnancy test for women of childbearing potential

- 
- Physical examination (including height and extra-articular assessments)
  - TB questionnaire
  - BASMI and spinal mobility
  - BASDAI
  - BASFI
  - SF-36
  - ASQoL
  - MOS Sleep Scale
  - EQ-5D
  - MASES
  - Total spinal pain NRS and nocturnal spinal pain NRS
  - Swollen and tender joint counts
  - PGADA
  - PhGADA
  - Productivity measures (WPS)
  - Resources utilization
  - Plasma for CZP concentration, anti-CZP antibodies, and biomarkers
  - Genetics/epigenetics, if applicable
  - Gene expression and proteomics, if applicable
  - Concomitant medication
  - AEs
  - Contact IXRS to randomize subject and to obtain kit number
  - Study drug administration (after all other visit assessments are completed and laboratory samples are drawn)

**8.3 Weeks 1, 2, 4, 6, 8, 10, 12, 14, 16, 18, 20, 22, 24, 26, 28, 30, 32, 34, 36, 38, 40, 42, 44, 46, 48, and 50 (all visits  $\pm 3$  days relative to Baseline)**

Assessments at these visits include:

- Vital signs; pulse rate, systolic and diastolic blood pressures and temperature (respiration rate will be assessed in addition if the subject experiences an AE) (at all on-site visits except Week 1)
- Blood samples will be collected for hematology, biochemistry, and CRP (Weeks 2, 4, 8, 12, 24, and 36 only)

- 
- CRP for the calculation of ASDAS (Weeks 16, 20, 28, 32, 40, 44, and 48)

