## 9.1 Assessment of efficacy variables

### 9.1.1 ASDAS

The ASDAS is comprised of a number of assessments which are scored by the subject and physician and multiplied by a proven formula (van der Heijde et al, 2009) as listed:

0.121 x Back pain (BASDAI Q2 result, see Section 9.1.5)

0.058 x Duration of morning stiffness (BASDAI Q6 result)

0.110 x PGADA (see Section 9.1.13)

0.073 x Peripheral pain/swelling (BASDAI Q3 result)

0.579 x (natural logarithm of the (CRP [mg/L] + 1))

Back pain, PGADA, duration of morning stiffness, peripheral pain/swelling and fatigue are all assessed on a numerical scale (0 to 10 units) (Lukas et al, 2009).

The variables related to ASDAS disease activity are defined as follows:

- ASDAS-Inactive Disease (ASDAS-ID): ASDAS <1.3
- ASDAS-Low Disease (ASDAS-LD): ASDAS  $\geq$ 1.3, <2.1
- ASDAS-High Disease Activity (ASDAS-HD): ASDAS  $\geq$ 2.1,  $\leq$ 3.5
- ASDAS-very High Disease Activity (ASDAS-vHD): ASDAS >3.5

The variables related to ASDAS improvement are defined as follows:

- ASDAS-Clinically Important Improvement (ASDAS-CII): ASDAS reduction (improvement) of  $\geq$ 1.1 relative to Baseline
- ASDAS-Major Improvement (ASDAS-MI): ASDAS reduction (improvement) of  $\geq$ 2.0 relative to Baseline

The ASDAS will be calculated at Screening, Baseline, Weeks 2, 4, 8, 12, 16, 20, 24, 28, 32, 36, 40, 44, 48, 52/WD, and Week 156/SFE-WD.

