### **14.3 Planned efficacy analyses**

The primary efficacy variable measurement for this study is based on ASDAS-MI response at Week 52. The associated primary outcome of the study will be defined as a composite endpoint that is achieved if a subject fulfills the following 2 components:

1. Remain in the study and on the double-blind study treatment through 52 weeks
2. Achieve an ASDAS-MI response at 52 weeks

For simplicity, this primary efficacy variable will be referred to as ASDAS-MI response at Week 52. However, the composite definition as described above will apply when this endpoint is analyzed. The primary analysis for this endpoint will be based on logistic regression. The odds ratio of the ASDAS-MI responder rates at Week 52 will be estimated and tested between treatment groups using a logistic regression model with factors of treatment group, region, and MRI/CRP classification (MRI+/CRP+; MRI+/CRP-; MRI-/CRP+). If the logistic regression

model is unable to converge, then the MRI/CRP classification variable may be dropped from the model to facilitate convergence. The study design is likely to result in some sites with a small number of enrolled subjects. The use of region as a stratification variable and as a factor in the model is intended to combine study centers in similar geographic regions. The geographic regions to be used will be defined in the IXRS and in the SAP. Given the composite endpoint definition described above, there will be no missing data for the primary endpoint, as subjects that discontinue the double-blind study treatment prior to Week 52 or who do not have an ASDAS-MI status at Week 52 are considered nonresponders to the double-blind study treatment.

As described in Section 6.3, subjects who discontinue the double-blind study treatment will not necessarily be withdrawn from the study. In an attempt to minimize missing data, efforts will be made to continue to collect safety and efficacy data on these subjects through study completion. Sensitivity analyses will be performed to evaluate the impact of missing data on the analysis of the primary efficacy variable (see Section 14.8).

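### Section 12 leaves CRP blinding optional after randomisation, although the investigator who may see the values can stop blinded treatment and so fix a primary non-response

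*Protocol*

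**What the plan says.** **CRP.** Protocol Section 12: "CRP will be collected and assessed either in a blinded or open manner". The list of visits that follows runs from Screening and the retest shortly before Baseline through Week 52/WD and the follow-up visit, so one either/or permission covers the pre-randomisation and all post-randomisation measurements. Section 8.3 draws CRP with hematology and biochemistry at Weeks 2, 4, 8, 12, 24 and 36, and adds "CRP for the calculation of ASDAS (Weeks 16, 20, 28, 32, 40, 44, and 48"). Table 12-1 places CRP in the routine serum biochemistry panel. Section 8.8 also allows CRP at unscheduled visits.

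**Blinding.** Section 7.9: "Pharmacokinetic and antibody data will be provided only after the study is unblinded". CRP is not named there. Sections 7.9.1 and 7.9.2 protect the allocation code and do not mention CRP either.

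**Switching and the endpoint.** Under Section 5.2, at any time but preferably not before Week 12, "the Investigator may discontinue the double-blind study treatment and start open-label treatment with either CZP" or another drug. Section 6.3 gives unsatisfactory response as a ground. Section 14.3 makes the first component of the primary outcome "Remain in the study and on the double-blind study treatment through 52 weeks", and adds that "subjects that discontinue the double-blind study treatment prior to Week 52 or who do not have an ASDAS-MI status at Week 52 are considered nonresponders".

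**The concern.** The protocol takes pains over blinding: unblinded injectors, sealed kits and a written blinding plan at each site. It then leaves undecided whether the investigator sees a routine laboratory marker that the drug is expected to change. A clear fall in CRP, or its absence, in a subject who entered with raised CRP may suggest the arm. The investigator who forms that view also decides whether blinded treatment continues, and free open-label CZP is on offer. Because stopping before Week 52 is itself failure on the primary outcome, a guess about treatment can enter the primary comparison directly. The first component of the endpoint is then only as objective as the investigator's blinding.

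**Working it through.** **1. The plan's own figure.** Section 14.10 gives 95% power for 40% versus 20% with 150 per arm at 2-sided 0.05. Pooled normal approximation: SE under the null = √(2 × 0.30 × 0.70 / 150) = 0.0529; SE under the alternative = √(0.24/150 + 0.16/150) = 0.0516; power = Φ((0.20 − 1.96 × 0.0529)/0.0516) = 96.9%, or 95.9% with continuity correction. The figure is reproduced and is not in question.

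**2. Who is exposed.** Section 7.10.2 sets a floor of 20% for each of MRI+/CRP+, MRI+/CRP− and MRI−/CRP+.
- Smallest CRP-positive share: 20% + 20% = 40%, or 120 of 300.
- Largest: 100% − 20% = 80%, or 240 of 300.

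In the remaining MRI+/CRP− subjects a CRP change carries little signal.

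**3. What is masked after randomisation.**

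| Result | Rule | Section |
|---|---|---|
| Pharmacokinetics, antibodies | Withheld until unblinding | 7.9 |
| CRP, Weeks 2 to 52 (14 scheduled visits) | Blinded or open, undecided | 12 |
| CRP, unscheduled visit | Investigator's discretion | 8.8 |

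**4. Route to the primary outcome.** Open CRP → suspicion of arm → discretionary stop (Sections 5.2, 6.3) → non-responder (Section 14.3). The last two links are explicit in the protocol; the first two are possible under it.

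**5. CRP is also part of the outcome.** ASDAS contains 0.579 × ln(CRP + 1) (Section 9.1.1). With assumed values, a fall from 15 to 3 mg/L contributes 0.579 × ln(16/4) = 0.80 units, which is 40% of the 2.0 needed for ASDAS-MI. A placebo subject heading for response may therefore show a falling CRP and look like a CZP subject.

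**6. Size and direction.** Let π be the responder rate without CRP-driven switching and s the fraction of would-be responders switched because of CRP, in the CZP (C) and placebo (P) arms. The observed difference is π_C(1 − s_C) − π_P(1 − s_P), so the bias is π_P·s_P − π_C·s_C. At the planned rates this is 0.20·s_P − 0.40·s_C. It is positive, favouring CZP, only if s_P exceeds twice s_C; with equal underlying rates, only if s_P exceeds s_C. On the odds-ratio scale of the primary model the weights differ, but the sign still depends on both fractions. The protocol gives neither fraction and no CRP distribution by arm, so no number can be put on the bias.

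**The case against.** The text permits open CRP; it does not prescribe it. It can be read as open before randomisation and blinded afterwards, and it speaks of assessing CRP rather than reporting it to sites. Section 7.6 requires a site blinding plan, and the Laboratory Manual may restrict reporting. Section 6.3 asks for contact with the Medical Monitor before a withdrawal where possible, and for the reason to be recorded. Subjects switched for poor response would mostly have failed anyway. Section 14.8 adds multiple imputation with post-discontinuation ASDAS set to missing, a tipping-point analysis and an observed-case analysis.

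Much of this stands as mitigation. The benign reading is possible, but the sentence does not say it. Section 7.6 does not mention CRP, and if the Laboratory Manual masks CRP then Section 12 still needs correcting to match. That only would-be responders matter is right, and is a main reason for giving no size. The three Section 14.8 analyses can show whether the result depends on counting switchers as failures; they cannot restore blinding. The further analysis using observed Week 52 data does not help much, since switched placebo subjects may by then be on open-label CZP.

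A reader might also infer bias through the physician's global assessment. That rating is not an ASDAS component, and Section 9.1.14 asks for it to be blinded, so it does not reach the primary outcome.

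**Conclusion.** The point holds as a risk left open by a badly fixed rule. Section 12 allows post-randomisation CRP to be open, Section 7.9 does not close the gap, and the route from a discretionary stop to primary non-response is written into the protocol. It concerns mainly the CRP-positive 40% to 80% of subjects. It would favour CZP if suspected placebo subjects were switched sufficiently more readily than CZP subjects.

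Two stronger readings should be resisted. One is that the investigators were unblinded: the protocol shows a permission, not what was reported. The other is that the false-positive rate is inflated by a calculable amount. Any such figure needs an assumed fraction of would-be placebo responders switched, with none on CZP, and the protocol gives no source for either. It also assumes no treatment difference in ASDAS-MI while CRP, an ASDAS component, separates the arms well enough to be recognised. Those assumptions sit badly together. This is a worthwhile, inexpensive correction to the blinding rules; it does not affect the sample size.

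**What to change.** In Section 12, replace the either/or phrase and reconcile it with Section 7.9 along these lines: CRP is open at Screening and 3 to 5 days before Baseline, for eligibility and stratification. Scheduled central-laboratory CRP results after randomisation through Week 52 are withheld from the investigator, blinded site staff, the subject and blinded sponsor staff until the Double-Blind Period database is locked. Unscheduled CRP under Section 8.8 remains available, and its use is documented.

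Section 14.10 records that enrolment was complete by Amendment 4, so masking cannot recover results already released. For those, record which post-randomisation CRP values each site saw and when, so that they can be set against the dates and reasons for stopping blinded treatment.

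Cost: a central-laboratory reporting setting, one sentence in each section, and the retrospective record. Downside: investigators do not see scheduled CRP when adjusting background therapy.

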## **12.1 Adverse events**

### **12.1.1 Definition of adverse event**

An AE is any untoward medical occurrence in a subject or clinical investigation subject administered a pharmaceutical product which does not necessarily have a causal relationship with this treatment. An AE can therefore be any unfavorable and unintended sign (including an abnormal laboratory finding), symptom, or disease temporally associated with the use of an IMP, whether or not related to the IMP.

If a surgical procedure is performed during the study participation, the underlying condition should be reported as the AE (eg, “appendicitis” is the AE resulting in appendectomy).

The following laboratory values and physical findings are also to be considered AEs:

- Laboratory value(s) that are out of reference range AND of clinical relevance, excluding Screening values
- Laboratory value(s) that change from a subject’s Baseline AND are of clinical relevance
- Pre-existing physical findings (including vital sign measurements) that worsen compared with Baseline AND that are “clinically important”

In order to ensure complete safety data collection, all AEs occurring during the study (ie, after signing the informed consent form), including any Screening and FU Periods required by the protocol, must be reported in the CRF even if no IMP was administered but specific study procedures were conducted. This includes all AEs not present prior to the Screening visit and all AEs which recurred or worsened after the Screening visit.

Signs or symptoms of the condition/disease for which the IMP is being studied should be recorded as AEs only if their nature changes considerably or their frequency or intensity increases in a clinically significant manner as compared to the clinical profile known to the Investigator from the subject’s history or the Baseline Period.

### **12.1.2 Procedures for reporting and recording adverse events**

The subject will be given the opportunity to report AEs spontaneously. A general prompt will also be given at each study visit to detect AEs. For example:

“Did you notice anything unusual about your health (since your last visit)?”

In addition, the Investigator should review any self assessment procedures (eg, questionnaires) employed in the study.

### **12.1.3 Description of adverse events**

When recording an AE, the Investigator should use the overall diagnosis or syndrome using standard medical terminology, rather than recording individual symptoms or signs. The CRF and source documents should be consistent. Any discrepancies between the subject’s own words on his/her own records (eg, diary card) and the corresponding medical terminology should be clarified in the source documentation.

Details for completion of the Adverse Event CRF (including judgment of relationship to study drug) are described in the CRF Completion Guidelines.

---

